6.5.3 Drug Interruptions

Conditions/events that may lead to study drug interruptions based on Investigator judgment and overall clinical assessment include:

- reported serious adverse event;
- emergency medical condition, unplanned hospitalization involving use of excluded concomitant medications;
- abnormal laboratory value(s) or abnormal test or examination result(s)

Should the participant interrupt the study drug for whatever reason, the re-start decision should be made on a case-by-case basis (refer to [Section 6.7.2](#)). Should the Investigator decide, after informing the Sponsor, to re-initiate treatment with study drug, depending on the duration of the interruption, the first dose at re-start may need to take place at the study site to ensure observation in a similar manner as on Day 1.

The reason for interruption of treatment and date of interruption should be appropriately documented in the source documents as well as in the appropriate eCRF.

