9.1 Discontinuation from study treatment and study

9.1.1 Discontinuation of study treatment

Discontinuation of study drug for a participant occurs when study drug is permanently stopped for any reason (prior to the planned completion of study drug administration, if any), and can be initiated by either the participant or the Investigator.

The Investigator must discontinue study treatment for a given participant if he/she believes that continuation would negatively affect the participant's well-being.

Discontinuation from study treatment is required under the following circumstances:

- Participant/guardian decision ([Section 9.2](#))
- Pregnancy ([Section 10.1.6](#) and [Section 10.1.7](#))
- Use of prohibited treatment ([Section 6.2.2](#))
- Diagnosis of PML
- Participants with active serious infections or reactivation (e.g. tuberculosis, hepatitis B or C)
- Skin and/or mucosal reactions which raise the suspicion of severe generalized major skin reactions (Stevens-Johnson syndrome, or toxic epidermal necrolysis-Lyell's syndrome)
- Hypersensitivity to the study medication
- Any situation in which continued study participation might result in a safety risk to the participant
- Protocol violation that results in a significant risk to the participant's safety
- Emergence of certain adverse events, such as malignancy (except successfully treated basal cell carcinoma, *in situ* squamous cell carcinoma and *in situ* carcinoma of cervix of uterus), liver failure or serious chronic infection (such as human immunodeficiency virus (HIV))
- Laboratory abnormalities (e.g. liver functions tests (LFTs) and abnormal test procedure defined in Appendix 1 ([Section 16.1](#)))
- Severe hypoproteinemia
- Interstitial lung disease or new onset or worsening of pulmonary symptoms, such as persistent cough and dyspnea, with or without associated fever, suspicious of interstitial lung disease
- Non-compliance with study drug or study procedures

Study treatment discontinuation should be considered under the following circumstances:

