16.3 Appendix 3: Safety Monitoring Guidance

16.3.1 Guidance on monitoring of Participants with symptoms of neurological deterioration suggestive of PML

Should a participant develop any unexpected neurological or psychiatric symptom/signs in the opinion of Investigator (e.g. cognitive deficit, behavioral changes, cortical visual disturbances or any other neurological cortical symptoms/signs any symptom/sign suggestive of an increase of intracranial pressure) or accelerated neurological deterioration, the Investigator should schedule a complete physical and neurological examination and an MRI as soon as possible before beginning any steroid treatment. Conventional MRI as defined in the protocol as well as additional scanning such as FLAIR and Diffusion-weighted imaging (DWI) sequences are recommended to aid in differential diagnosis. The local neuro-radiologist must evaluate the MRI. The Investigator will contact the Medical Advisor at Novartis and a clinical trial team (CTT) member to discuss findings and diagnostic possibilities as soon as possible. A copy of the unscheduled MRI should be sent to the MRI Evaluation Center designated by Novartis as soon as possible. AE/SAEs need to be filed as appropriate.

If the MRI shows new MS lesions consistent with an MS relapse, assessment and treatment of the relapse will be performed as described in the protocol ([Section 6.2.3](#) and [Section 8.3.1](#)). In case of new findings in the MRI images in comparison with the previous available MRI, which are not compatible with MS lesions, the study drug will be discontinued and other diagnostic evaluations need to be performed at the discretion of the Investigator. If new lesions are detected on the MRI, which may be infectious in origin, it is recommended to collect a cerebrospinal fluid sample if indicated. Analysis of the Cerebrospinal Fluid (CSF) sample including cellular, biochemical, Polymerase Chain Reaction, and microbiological analysis (e.g. herpes virus, JC virus) to confirm/exclude an infection should be performed. In the event of suspected CNS

infection (PML), a CSF aliquot should be sent to a central laboratory (designated by Novartis) for confirmatory testing.

Only after the evaluations have excluded diagnoses other than MS and after discussion with the Medical Advisor at Novartis and a CTT member, the study drug may be restarted.

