16.3.2 Guidance on monitoring Participants with infections

All infections that develop during the study will be reported as AEs on the respective AE eCRF pages. Treatment and additional evaluations will be performed at discretion of the Investigator.

The Investigator should remind the participant of the risk of infections and instruct them to report any symptoms of infections promptly to the Investigator. The participants must also be reminded to always carry their participant Information Card (with site contact information and which identifies them as participants in a clinical study with investigational and control agents with potential immunosuppressive effects) and to show this to any local healthcare provider they may consult and ask that the Investigator be contacted.

In the case of suspected or confirmed serious (CTCAE, Grade 3-4) or atypical infection, study drug interruption should be considered. The Investigator should inform the Novartis Medical Advisor and/or a CTT member of any such cases.

When evaluating a participant with a suspected infection, the most sensitive tests available should be used (i.e. that directly detect the pathogen, as with polymerase chain reaction).

The Investigator should consider early treatment with specific antimicrobial therapy based on clinical diagnosis or suspicion thereof in consultation with infectious disease experts, as appropriate. The Investigator should inform the Novartis Medical Advisor and CTT of any such cases.

Investigators should consider the added immunosuppressive effects of corticosteroid therapy for treatment of MS attack/relapse and increase vigilance regarding infections during such therapy and in the weeks following administration.

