In participants with known malignancies treated with ofatumumab, cases of fatal hepatitis B virus (HBV) reactivation and fatal infection due to hepatitis B in participants who have not been previously infected have occurred (refer to local Arzerra® prescribing information). The MS participants enrolled in the study who are at potential risk of HBV reactivation (e.g. Participants with evidence of prior HBV infection (antibody to hepatitis B surface antigen (anti-HBc) positive and Hepatitis B surface antigen (HBsAg) negative) and whose HBV deoxyribonucleic acid (DNA) test is negative at Screening, should be closely monitored for signs of active HBV infection or reactivation during the study. In participants with suspicion of HBV infection (active/reactivation), laboratory testing for HBV should be done. For participants who show evidence of hepatitis B infection (HBsAg positive [regardless of antibody status] or HBsAg negative but anti-HBc positive), the Investigator is advised to consult with physicians with expertise in managing hepatitis B regarding monitoring and consideration for HBV antiviral therapy.

In participants who develop reactivation of HBV while receiving study drug, immediately discontinue study drug and institute appropriate treatment and follow-up.

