## **2.7.2 Statistical hypothesis, model, and method of analysis**

The following statistical analyses are planned for the secondary endpoints:

1. Retention on study treatment from baseline to Month 6, and to Month 12 (Yes, No) will be summarized using frequency counts and percentages for the FAS. Retention will be based on the number of study drug discontinuations.
2. Biomarker analysis – See [Section 2.12.1](#)
3. C-SSRS analysis – See [Section 2.8.3.1](#)
4. TSQM-9 analysis – See [Section 2.11.1](#)
5. TEAEs analysis – See [Section 2.8.1](#)

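### For a confirmed, active Grade 3-4 infection, Section 9.1.1 requires a permanent stop while Appendix 16.3.2 only asks that interruption be considered, and nothing ranks the two

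*Protocol*

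**What the plan says.** Protocol Section 9.1.1 first fixes the term: "Discontinuation of study drug for a participant occurs when study drug is permanently stopped for any reason". It then gives a list under the words "Discontinuation from study treatment is required under the following circumstances". One entry is "Participants with active serious infections or reactivation (e.g. tuberculosis, hepatitis B or C"). The section does not define serious.

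Appendix 16.3.2 says: "In the case of suspected or confirmed serious (CTCAE, Grade 3-4) or atypical infection, study drug interruption should be considered". For hepatitis B it is stricter: "In participants who develop reactivation of HBV while receiving study drug, immediately discontinue study drug and institute appropriate treatment and follow-up".

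Section 6.5.3 names a reported SAE among the events that may lead to interruption on the investigator's judgment. After any interruption, "the re-start decision should be made on a case-by-case basis".

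Appendix 16.3.1 deals with new MRI findings "which are not compatible with MS lesions, the study drug will be discontinued". Its last paragraph allows the drug to be restarted once diagnoses other than MS have been excluded.

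On the analysis side, SAP Section 2.7.2 states: "Retention will be based on the number of study drug discontinuations". SAP Section 2.5.2 scores a participant without a valid Month 12 MRI as a non-responder and leaves out MRIs taken after the efficacy cut-off.

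**The concern.** Infection is a risk the protocol returns to repeatedly, asking for added vigilance in Table 6-1, Section 6.2.3 and Appendix 16.3.2. For its serious form, one section makes a permanent stop compulsory and another treats even a temporary stop as something to weigh. Neither refers to the other, and no text says which prevails.

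The two also use the word serious differently. Appendix 16.3.2 ties it to severity grade. Section 10.1.2 defines a serious event by outcome or medical significance. Section 9.1.1 does neither.

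The first thing at stake is a consistent safety instruction. The second is the endpoints. A discontinued participant counts against retention and, depending on timing, may be imputed as a non-responder. The same participant, interrupted and resumed, can count as a success on both. Part of the variation in two endpoints could then reflect which section a site applied.

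**Working it through.** **1. The texts side by side.**

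| Case | Section 9.1.1 | Appendix 16.3.2 and Section 6.5.3 | Consistent? |
|---|---|---|---|
| Hepatitis B reactivation | Permanent stop required | Immediate discontinuation | Yes |
| Confirmed, active Grade 3-4 infection that also meets an SAE criterion, not hepatitis B reactivation | Permanent stop required, in either sense of serious | Consider interruption; restart decided individually | No |
| Confirmed, active Grade 3-4 infection that meets no SAE criterion | Depends on what serious means | Consider interruption | Only if serious in 9.1.1 means the SAE sense |
| Grade 1-2 infection that meets an SAE criterion | Required only if serious means the SAE sense | 16.3.2 does not reach it unless atypical; 6.5.3 permits interruption | Undetermined |
| Suspected or atypical infection, not confirmed as serious | Not clearly triggered | Consider interruption | No conflict |

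The second row is the firm contradiction. The third and fourth follow from the missing definition. Tuberculosis and hepatitis C, the other examples in 9.1.1, have no specific line in 16.3.2 and fall under its general sentence if Grade 3-4 or atypical.

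**2. The plan's own precision.** Inputs: n=100 and proportions of 75%, 80% and 85% (Protocol 12.8.1, SAP Section 3); normal-approximation 95% interval (SAP 2.5.2). The half-width is 1.96 × √(p(1−p)/100).

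- p=0.75: 8.49 points (plan: 8.5)
- p=0.80: 7.84 points (plan: 7.8)
- p=0.85: 7.00 points (plan: 7.0)

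The stated figures reproduce.

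**3. Retention.** Each participant stopped under one reading and resumed under the other changes the count by one: 1/100 = 1 percentage point.

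**4. Primary proportion.** The efficacy cut-off is 30.4375 days after the last dose (SAP 2.1.1.8). The Month 12 MRI window is Days 321 to 427 (SAP Table 2-4). An MRI must be inside the window and not after the cut-off, so the last dose must fall no earlier than 321 − 30.4375 = 290.6, that is, Day 291. By the scheduled days in SAP Table 2-1, a last dose at Month 9 (Day 275) or before cannot yield a valid Month 12 MRI, and the outcome is imputed as No. A last dose at Month 10 (Day 305) or later can still yield one, because an MRI is required at the end-of-study visit. This takes the Table 2-4 window as governing, although SAP 2.4.2.2 notes that an early discontinuer's final MRI is recorded under the Month 12 label.

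The shift is therefore at most 1/100 = 1 point per participant, and zero if the stop is late enough or the participant would not have responded anyway.

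**5. What one participant does.** At 85% the interval is 85 ± 7.00, or 78.0% to 92.0%. With one responder turned into an imputed non-responder, the estimate is 84% and the half-width is 1.96 × √(0.84 × 0.16/100) = 7.19 points, giving 76.8% to 91.2%.

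**6. How many participants.** For k participants, retention moves by k points and the primary proportion by 0 to k points. The documents do not give k.

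**The case against.** A reader might infer that a site cannot follow both texts. That goes too far. A site that discontinues breaches neither, because a line asking for interruption to be considered does not forbid a permanent stop. A site that interrupts on suspicion and discontinues on confirmation also satisfies both. Section 6.5.3 is a general permissive rule and does not override a specific mandatory list; its part here is to supply a restart route once a site has chosen interruption.

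A reader might confine the 9.1.1 entry to infections like tuberculosis or hepatitis, which would shrink the conflict. The examples are introduced as non-exhaustive, however, and active serious infection is set out as an alternative to reactivation, so the text does not impose that limit.

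A reader might see Appendix 16.3.1 as the same conflict for suspected PML. Its trigger is new MRI findings not compatible with MS, and Section 9.1.1 requires a stop on a diagnosis of PML, so no diagnosed case is restarted. What remains is a loose use of discontinued for a stop that can be reversed.

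There is also central visibility: the investigator is asked to inform the medical advisor or a trial team member of such infections, and a restart follows informing the sponsor. This makes divergence easier to see but does not say which rule applies.

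On size, a reader might infer a shift of several points. The only rate cited is 1.3% serious infections on ocrelizumab (Section 4.5), from pivotal trials that Section 1.1 describes as running over 2 years. At an even rate that is 1.3/2 = 0.65 per 100 in 12 months, in a different population. The observed-data analysis does not impute these participants as No, and no hypothesis is tested, so no decision threshold is at risk. These limits on size stand.

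**Conclusion.** The protocol is wrong as written on this point. For a confirmed, active Grade 3-4 infection other than hepatitis B reactivation, it gives a mandatory permanent stop and a discretionary interruption without ranking them, and its use of serious does not settle which participants fall under which rule. The clearest case is an infection that is both Grade 3-4 and an SAE.

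Similar participants could be handled differently across sites; the documents do not show that any were. The size is 1 percentage point of retention per participant affected at n=100, and up to 1 point of the primary proportion under non-responder imputation. The latter assumes a last dose before about Day 291, a participant who would otherwise have responded, and the Table 2-4 window as governing. The number affected is unknown, so no total shift can be stated. The main reason to act is the unclear safety instruction; the effect on the estimates is secondary.

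**What to change.** Reconcile Section 9.1.1 and Appendix 16.3.2 so that one action applies to a serious infection, and add a cross-reference from Section 6.5.3. Define serious infection once, by severity grade or by the Section 10.1.2 criteria, and use that definition throughout. In Appendix 16.3.1, make the term for stopping the drug agree with the later permission to restart, since Section 9.1.1 makes discontinuation permanent. Which rule and which definition stand is for the clinical team.

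The cost is wording in four places (9.1.1, 6.5.3, 16.3.1 and 16.3.2) and a note to sites, with no new assessments. If dosing has already ended, list the participants with a Grade 3-4 or serious infection, with the action taken, retention status and Month 12 outcome, beside the retention and primary results. The inputs are already collected: Section 10.1.1 records the action taken with study treatment, and SAP 2.8.1 separates events leading to interruption from those leading to permanent discontinuation.

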9.1.2 Discontinuation from study

Discontinuation from study is when the participant permanently stops receiving the study treatment, and further protocol-required assessments or follow-up, for any reason. If the participant agrees, a final evaluation at the time of the participant's study discontinuation should be made as detailed in the assessment table (refer to Section 8).

9.1.3 Lost to follow-up

For participants whose status is unclear because they fail to appear for study visits without stating an intention to discontinue from study treatment or discontinue from study or withdraw consent/oppose to the use of their data/biological samples, the Investigator must show "due diligence" by documenting in the source documents steps taken to contact the participant, e.g. dates of telephone calls, registered letters, etc. A participant should not be considered as lost to follow-up until due diligence has been completed or until the end of the study.

9.2 Withdrawal of informed consent/Opposition to use

Participants may voluntarily withdraw consent to participate in the study for any reason at any time. Withdrawal of consent occurs only when a participant:

- Does not want to participate in the study anymore, and
- Does not allow further visits or assessments, and
- Does not want any further study related contacts

This request should be in writing (depending on local regulations) and recorded in the source documentation.

In this situation, the Investigator should make a reasonable effort (e.g. telephone, e-mail, letter) to understand the primary reason for the Participant's decision to withdraw his/her consent/opposition to use data/biological samples and record this information.

Where consent to the use of personal and coded data is not required, participant therefore cannot withdraw consent. However, they still retain the right to object to the further collection or use of personal data.

Study treatment must be discontinued and no further assessments conducted, and the data that would have been collected at subsequent visits will be considered missing.

Further attempts to contact the participant are not allowed unless safety findings require communicating or follow-up.

All efforts should be made to complete the assessments prior to study withdrawal. If the participant agrees, a final evaluation at the time of the participant's withdrawal of consent/opposition to use data/biological samples should be made as detailed in the assessment table ([section 8](#))

Novartis will continue to retain and use all research results (data) that have already been collected for the study evaluation including processing of biological samples that has already started at the time of consent withdrawal/opposition. No new Personal Data (including biological samples) will be collected following withdrawal of consent/opposition according to applicable law.

[figure not shown]
For US: All biological samples not yet analyzed at the time of withdrawal may still be used for further testing/analysis in accordance with the terms of this protocol and of the informed consent form.

9.3 Study completion and post-study treatment

Study completion is defined as when the last participant finishes their Study Completion visit and any repeat assessments associated with this visit have been documented and followed-up appropriately by the Investigator or, in the event of an early study termination decision, the date of that decision.

A participant is considered to have completed the study when they fulfill the following criteria:

- Participant has completed the study in its entirety according to the approved duration of the study within that country

- The participant has **not** stopped the study due to one or more of the following reasons:
 - Discontinuation of study treatment (Section 9.1.1)
 - Withdrawal of informed consent (Section 9.2)
 - Lost to follow-up (Section 9.1.3)

End of Study (EOS) visit is mandatory for all participants. For participants that complete the study, the next (and last) scheduled visit is the EOS visit and should align with the overall visit schedule. Participants will then enter the Safety Follow-up according to the assessment schedule in Table 8-2 if they do not initiate a commercial MS disease modifying therapy. Participants who prematurely discontinue study treatment will have their EOS visit as soon as possible and continue into the Safety Follow-up for 6 months according to the assessment schedule in Table 8-2 if they do not initiate a commercial MS disease modifying therapy.

The Investigator must provide follow-up medical care for all Participants who are prematurely withdrawn from the study, or must refer them for appropriate ongoing care.

